## 4 STUDY OBJECTIVES AND HYPOTHESES

This Phase II study will be undertaken to determine the presence and degree of  $^{99m}\text{Tc}$ -rhAnnexin V-128 uptake at sites of clinical disease in patients with clinical suspicion or confirmed diagnosis of SpA. While the majority of these patients will be diagnosed with AS, there will be a substantial number of patients diagnosed with other types of disease including IBD related SpA and Psoriatic arthritis. We hypothesize that SpA patients with active disease as manifested clinically by dull low back, buttock or hip pain will have significant increased  $^{99m}\text{Tc}$ -rhAnnexin V-128 uptake in the sacroiliac joints and/or spine which will correlate with both clinical scoring and changes with T1 and STIR without contrast MRI findings. We also hypothesize that we will be able to directly quantify the severity of inflammation at sites of disease with a higher degree of specificity and sensitivity than MRI, CT and plain film radiography.

Eligible patients after obtaining informed consent, baseline blood labs, and urinalysis, will be injected once with  $^{99m}\text{Tc}$ -rhAnnexin V-128 followed by SPECT/CT imaging of the lumbosacral spine, sacroiliac joints and abdomen at 60 min and 2 hrs after injection of the radiotracer. Patients will undergo also a whole body planar scan and spot views on specific areas at the same time-points (spot views may not be repeated at T+2hrs). An optional whole body planar scan will be done 24hrs post injection for 5 patients as well as spot views, if deemed appropriate by the investigator.

**Study Protocol**

Knowledge of the expected dynamic range of the disease related changes in  $^{99m}\text{Tc}$ -rhAnnexin V-128 uptake in correlation with clinical measured of disease severity within affected joints will be critical for the power calculations and sample size estimates as part of the design of a follow up studies in SpA patients in order to further demonstrate the benefit of this new imaging procedure versus conventional imaging with MRI and plain film radiography. Furthermore, it is expected that the quantitative capabilities of SPECT/CT and the inherent sensitivity of  $^{99m}\text{Tc}$ -rhAnnexin V-128 imaging and reduced cost will replace MRI as a screening tool for the work up of patients with SpA.

As secondary goal, we also wish to determine the ability (specificity) of  $^{99m}\text{Tc}$ -rhAnnexin V-128 to distinguish between active autoimmune arthritis versus osteoarthritis particular of the lumbosacral spine and SI joints of patients with SpA. We also hypothesize that some of SpA patients with active disease have subclinical Crohn's disease. Therefore, we wish to perform a pilot study on the localization of  $^{99m}\text{Tc}$ -rhAnnexin V-128 in the abdomen.

### **4.1 Study objectives**

Primary Objective:

- To determine the magnitude and dynamic range of  $^{99m}\text{Tc}$ -rhAnnexin V-128 uptake in disease affected sacro-iliac or lumbar spine joints in patients with clinical suspicion or confirmed diagnosis of SpA.

Secondary Objectives:

- To determine clinical utility of  $^{99m}\text{Tc}$ -rhAnnexin V-128 SPECT imaging in the identification of chronic osteoarthritic active sites of SpA patients compared with MRI in patients with disease-affected sacro-iliac or lumbar spine joints.
- To assess the presence of antibodies against rhAnnexin V-128 at baseline and post-treatment
- To determine the localization pattern and magnitude of focal uptake of  $^{99m}\text{Tc}$ -rhAnnexin V-128 within the abdomen in patients with clinical suspicion or confirmed diagnosis of Spondyloarthritis (SpA).

### **4.2 Study hypotheses**

We hypothesize that  $^{99m}\text{Tc}$ -rhAnnexin V-128; a second generation form of  $^{99m}\text{Tc}$  radiolabeled annexin V with significantly higher PS binding affinity and improved in vivo localization properties, will be highly specific in imaging degenerative osteoarthritis particularly of the lumbosacral spine

**Study Protocol**

and sacroiliac joints as seen by SPECT/CT in patients with SpA. We also hypothesize that  $^{99m}\text{Tc}$ -rhAnnexin V-128 will be localized within the abdomen of SpA patients with active disease showing suspicious Crohn's disease.

### ***4.3 Study justification***

At the completion of this study, we will have preliminary data on the expected magnitude and dynamic range and specificity of  $^{99m}\text{Tc}$ -rhAnnexin V-128 uptake at sites of active disease in SpA patients at presentation.

## **5 STUDY DESIGN**

### ***5.1 Study Outline***

This is a monocentric, open label, PoC, Phase II study. Patients who have signed the informed consent and are eligible for study participation according to the inclusion and exclusion criteria will receive a single intravenous bolus of  $^{99m}\text{Tc}$ -rhAnnexin V-128 on Day 0 followed by SPECT/CT of the sacro-iliac joints, spine and abdomen at 60 min and 2hrs after injection of the radiotracer within 14 days after screening in order to minimize the potential delay in changing NSAID therapy or non-biologic DMARD or the start of non-biologic DMARD or biologic DMARD (excepted for the first 5 enrolled patients who will not be eligible for the start of biologic DMARD). Patients will undergo also a whole body planar scan and spot views on specific areas at the same time-points (spot views may not be repeated at T+2hrs). We will also perform T1 and STIR without contrast MRI of the sacro-iliac joints and lumbar spine within this same time window,

Details on study assessments are provided in Protocol Section 8 and Table1.

### ***5.2 Study duration and End of Study***

Study duration is maximum 7 weeks (including the screening period) for each patient. The end of the study is defined as the moment that the last enrolled patient has completed the planned assessments at Day 30.

## **6 PATIENT SELECTION**

Approval for the study will be obtained from the local IRB of Cedars-Sinai Medical Center Office of Research of Compliance. All patients will provide written informed consent prior to the initiation of any study procedures.

### ***6.1 Inclusion Criteria***

**For the first 5 patients enrolled in the POC part:**

1. Patients with clinical suspicion or confirmed diagnosis of SpA, based on the ASA criteria with active symptoms including back, hip or buttock pain prior to:

**Study Protocol**

- A change in NSAID therapy or
- A change in non-biologic DMARD or
- A start of non-biologic DMARD.

**For the next 15 patients enrolled in the Phase II part:**

1. Patients with clinical suspicion or confirmed diagnosis of SpA, based on the ASAS criteria with active symptoms including back, hip or buttock pain prior to:
  - A change in NSAIDs therapy
  - A change in non-biologic DMARD
  - A start of non-biologic DMARD
  - A start of biologic DMARD

**For all patients:**

2. Age over 18 years old.
3. Signed Informed Consent Form

**6.2 Exclusion Criteria**

1. Pregnancy or lactation
2. Liver impairment (ALT, AST or Bilirubin > 2 ULN) at screening visit or baseline
3. Kidney impairment (serum creatinine > 1.5 mg/dL)
4. History of any disease or relevant physical or psychiatric condition or abnormal physical finding which may interfere with the study objectives at the investigator judgment
5. Known hypersensitivity to the investigational drug or any of its components
6. Contraindication(s) to the MRI procedure (claustrophobia, prosthetic valve, pacemaker, inability to lie still in a supine position)
7. Participation to another clinical trial within 4 weeks before study inclusion except for patients who have participated or who are currently participating in an interventional study without any study drug administration.

**6.3 Number of patients**

Up to twenty evaluable patients will be recruited.

**6.4 Patients Identification**

Each patient will be anonymized and identified with a patient ID number. A unique patient identification number (Patient ID) will be assigned at the start of the screening period to each patient who signs the informed consent form until the study termination of the patient. This number will identify the subject throughout the study. Patient IDs will include the 2-digit protocol number (03), the 2-letter country code (US) and a 3-digit patient number (ex: 03-US001 for first subject in).

**Study Protocol****6.5 Premature Discontinuation**

The withdrawal of a study patient is mandatory in the following cases:

- Pregnancy
- Protocol violation determined as critical
- Lost to follow-up
- Serious intercurrent illness or other safety reasons for what the Investigator considers it is in the best interest of the participant to withdraw from the study
- Screening failure

A “screening failure” is a patient who has signed the informed consent, but who does not meet all selection criteria following the screening evaluations. For patients not considered eligible after the screening period, the reason for not being eligible must be documented. No additional assessments are needed. Patient information collected at the Screening visit will be entered in the e-CRF and will be used in the study analysis.

Patients who will not have received the study product will be replaced.

The patient is free to withdraw from the study for any reason and at any time without giving reason for doing so and without penalty or prejudice. It is also possible that the Sponsor or the regulatory authorities request termination of the study if there are concerns about conduct or safety.

The primary reason for a patient’s withdrawal from the study should be determined as possible. The date and reason for discontinuation must be documented in the e-CRF.

**6.6 Prohibition and Restrictions**

The most important required restriction for study patients is pregnancy. Pregnancy tests will be performed for all patients (of child bearing potential) at baseline and prior to the radiotracer administration.

Imaging is performed ambulatory. After imaging, patient may go back home or go back to work without particular precaution for him or his relatives.

Any concomitant medication deemed necessary for the welfare of the subject during the study may be given at the discretion of the Investigator. However, it is the responsibility of the Investigator to ensure that details regarding the medication are recorded in full in the case report form, including any changes that have occurred during the study.

**7 STUDY MEDICATION AND TREATMENT****7.1 Packaging and Labelling**

The full name of the Investigational New Drug is “Kit for the Preparation of Tc-99m Recombinant Human Annexin V-128 for Injection”. The kit will be prepared, packaged and released according to Sponsor Standard Operating Procedures (SOPs), and in compliance with the principles of the Good Manufacturing Practice (GMP) guidelines, ICH Good Clinical Practice (GCP) guidelines, and

applicable federal, state and local laws/regulations.

The investigational product will be supplied by the Sponsor as a sterile, single vial lyophilized kit for reconstitution with  $^{99m}\text{Tc}$  solution.

A single dose vial contains an amount of rhAnnexin V-128 and excipients suitable for preparing up to 740 MBq of injectable  $^{99m}\text{Tc}$ -rhAnnexin V-128. The excipients in the kit are the following: stannous chloride (reducing agent), sodium  $\alpha$ -D-Glucoheptonate dihydrate (transchelating agent), gentisic acid sodium salt hydrate (radiation stability enhancer), hydroxypropyl- $\beta$ -cyclodextrin (solubilizer), sodium metabisulfite (antioxidant) and trehalose dihydrate (lyoprotectant and cake-forming agent). Lactic acid is also present as buffering agent.

The reconstitution procedure and the specifications of the kit and of the radiolabeled imaging agent are described in Appendix I.

## **7.2 Handling of Study Medication**

$^{99m}\text{Tc}$ -rhAnnexin V-128 must be administered at the investigational site. The study medication must be stored, handled and administered only by qualified/authorized personnel and must be prepared in accordance with pharmaceutical quality requirements, and radiation safety regulations.

Based on the stability tests performed (Appendix I), the Annexin Kit can be stored upon receipt at  $5^{\circ}\text{C} \pm 3^{\circ}\text{C}$  until the expiry date stated on the labels.

A single dose vial containing 0.4 mg of lyophilized rhAnnexin V-128 will be reconstituted with 2 mL  $\pm$  0.2 mL containing 740 MBq  $\pm$  74 MBq (20 mCi  $\pm$  2 mCi) of  $^{99m}\text{Tc}$  from the generator. This amount of radioactivity provides a sufficient amount of radioactivity for QC testing and the foreseen  $^{99m}\text{Tc}$ -rhAnnexin V-128 dose of  $350 \pm 10$  % MBq for up to 4 h after labelling. The administration volume (corresponding to  $350 \pm 10$  % MBq) is calculated according to the estimated time of injection, on the basis of the physical decay of the radionuclide (half-life = 6.02 h). Stability studies have demonstrated radiochemical purity at 6 h from labelling greater than 90%, which is in line with current specifications of the Kit for the preparation of  $^{99m}\text{Tc}$ -rhAnnexin V-128 for injection. For the purpose of this study, it is recommended to administer the reconstituted solution within 4 hours after completion of the labelling reaction. It is also required to determine the amount of radioactivity injected to the patient by measuring the radioactivity before and after injection with an appropriate radioactivity calibration system.

## **7.3 IMP Packaging and Storage**

The site personnel will maintain shipping, dispensing, and collection logs. All investigational product will be stored and inventoried according to the protocol instructions and applicable federal, state, and local regulations and will be stored in a secure, locked location with limited authorized access at the investigational site.

## **7.4 Precautions and recommendation for use**

Technetium-99m eluate should be obtained from a commercially available Mo-99/Tc-99m generator, approved by regulatory authorities, that has been eluted within the past 24 hrs. The radiopharmacist will be directed to use the eluate within one hour of milking the generator.

On ongoing basis the Investigator/radiopharmacist agrees to conduct a study medication supply inventory and to record the results of this inventory on the IMP Reconciliation Form. It must be possible to reconcile delivery records with those of used and unused medication. Any discrepancies must be accounted for. Appropriate forms of deliveries and returns must be signed by the responsible person.

Unused "Kits for preparation of  $^{99m}\text{Tc}$ -rhAnnexin V-128 for injection" will be locally discarded after monitoring by the Clinical Research Associate (CR A).

Refer to Appendix I for detailed instruction on the Radiolabeled Imaging Product  $^{99m}\text{Tc}$ -rhAnnexin V-128, Cautionary notes, Analytical and Biological Controls, Stability and Shelf Life.

### **7.5 Study Medication Dose, Mode of Administration, Batch Number**

The "Kit for preparation of  $^{99m}\text{Tc}$ -rhAnnexin V-128 for injection" consists of 1 patient dose. The single dose vial (0.40 mg rh-Annexin V-128) will be reconstituted with 2 mL  $\pm$  0.2 mL containing 740 MBq  $\pm$  74 MBq (20 mCi  $\pm$  2 mCi) of  $^{99m}\text{Tc}$ .

The labelling reaction requires 90 minutes and the reconstituted radiolabeled product is stable for 6 h. For the purpose of this study, it is recommended to administer the reconstituted solution within 4 hours after completion of the labelling reaction. Patients will receive a single administration of  $^{99m}\text{Tc}$ -rhAnnexin V-128 on Day 0. When the investigational product is received at the site, the investigator, pharmacist or authorized designee shall check for accurate delivery and acknowledge receipt by signing and dating the documentation provided by the Sponsor and returning it to the Sponsor or designee. A copy of this documentation shall be retained for the Investigator file.

The dispensing of the investigational product shall be carefully recorded on an investigational product accountability form provided and an accurate accounting must be available for verification by the CRA at each monitoring visit.

Unused investigational product must not be discarded or used for any purpose other than the present study. The CRA will periodically collect the Drug Accountability Forms and will check all investigational product (both unused and used) before making arrangements for authorizing their destruction at the investigational site.

## **8 ASSESSMENTS**

Voluntary written informed consent will be obtained prior to the initiation of any study-related procedures. Study conduct procedures will include screening, the imaging visit and follow-up visits.

### **8.1 Baseline Assessments**

- Each patient's demography: gender, ethnicity, medical history, and relevant baseline characteristics will be recorded at Screening visit.

## Study Protocol

- Inclusion/exclusion criteria will be checked at Screening.
- Women of childbearing potential must have negative urine pregnancy test at Screening before the radiotracer administration and before MRI (in case the MRI is not performed on the same day of the screening visit).
- Vital signs will be taken at Screening.
- Physical examination will be conducted at Screening.
- BASDAI, BASFI, BASMI and MASES assessments will be performed.

### 8.2 Safety Assessments

- Physical examination will be conducted at D30
- Measurement of vital signs (systolic and diastolic blood pressure and heart rate) will be performed 15 minutes before the radiotracer administration and at the end of the last imaging procedure at Day 0.
- Women of childbearing potential must have negative urine pregnancy test before injection of the radiotracer at Day 0.
- All medications taken from 2 weeks prior to the administration date through the end of study are to be recorded as prior and concomitant medications, including therapies for SpA.
- Any adverse events occurring during the course of the study will be reported and recorded in the eCRF. 24 hours after treatment injection (at Day 1), each patient will be called in order to inquire if they experienced signs or symptoms such as edema, rash or have any clinical findings.

### 8.3 Standard Laboratory Assessments

General laboratory analysis will be performed and blood samples will be collected at screening and at Day 30.

Blood sample will be drawn and urine will be collected as mentioned in the study chart. A total volume of 50 mL, including blood sample for immunogenicity assessment, will be collected during the study for each patient.

Hematology	Coagulation	Blood Chemistry	Urinalysis

 
• WBC with differential
 
• RBC
 
• Platelets
 
• Hb
 
• MCV
 
• Hematocrit
 
	
 
• PT
 
• PTT
 
• INR
 
	
 
• BUN
 
• Serum creatinine
 
• Uric acid
 
• Albumin
 
• Total bilirubin
 
• Direct bilirubin
 
• AP
 
• AST/ASAT
 
	
 
• Dipstick test
 
• Pregnancy test (at screening and before injection of study product)
 

		
 
• ALT/ALAT
 
• Gamma-GT
 
• Sodium
 
• Potassium
 
• LDH
 
• CRP
 
• Calcium
 
• Glucose
 
• Chloride
 
• Phosphorus
 
• Total cholesterol
 
• Total protein
 
	
--	--	---------------------------------------------------------------------------------------------------------------------------------------------------------------------------------------------------------------------------------------------------------------------------------------------	--

In case one of the assessments of the dipstick test is positive, a microscopy analysis of the urine must be performed.

### **8.4 Clinical assessment**

A clinical evaluation including the search for enthesopathy – using the Maastricht Score (MASES) - and assessments with BASDAI, BASFI and BASMI will be performed at Screening.

The clinical assessment will be completed by the measurement of biological markers of inflammation (CRP and CBC) at Screening and at Day 30.

### **8.5 Imaging**

Patients will be injected intravenously with 350 ± 10 % MBq of 99mTc-rhAnnexin V-128 with an 18 gauge angiocath IV and saline TKO drip set up placed in the antecubital fossa.

Bone Lumbar Spine SPECT/CT, SI SPECT/CT and abdomen SPECT/CT will be performed 60 minutes and 2 hours after injection of radiotracer followed by a whole body planar scan and spot views on specific areas at the same timepoints (spot views may not be repeated at T+2 hrs if deemed unnecessary)

The Infinia™ Hawkeye 4 SPECT/CT (GE Healthcare) scanner was used for patients with the following parameters; start at 0°, 180° rotation/detector, 64 steps, 3° per step, 30 sec per step, overall ARC 360°, (scan time = 23 minutes) 128 x 128, multi-purpose collimator (Skylight) in 1 x zoom mode. An attenuation and diagnostic CT scan will be performed on the lumbar spine using a 512 x 512 matrix, 140 keV, 2.5 mA, axial 1 sec, 5 mm slices.

Semi-quantitative assessment of inflammatory joints and abdomen will be performed in terms of TBR as well as by calculating the relative uptake in ROI/VOIs. ROI and VOI defined and use in the different scintigraphies will strictly have the same pixel size and localization; and will be measured in counts.

In case a suspected anomaly is found at imaging, it would be reported to the rheumatologist and the patient's general practitioner.

A whole lumbar spine and sacro-iliac joint MRI will be performed within 14 days of 99mTc-annexin V-128 scanning using the following parameters: **SI Joint Sequences** /3 plane localizer / Whole pelvis

Coronal T1/ Whole pelvis Coronal T2 FS. Small FOV over SI Joints (~20 cm FOV): Sequences /Obl Axial T1. Obl Axial T2 FS (May use STIR or IDEAL for poor FS), Obl Coronal T1, Obl Coronal T2, FS (May use STIR or IDEAL for poor FS). Following pre/post sequences will be used to help assess for subtle sacroilitis: Obl Ax T1 FSE FS Pre / Obl Ax T1 FSE FS Post /Obl Cor T1 FSE FS Post. FOV notes: Small FOV width should be approximately from femoral head to femoral head; Oblique axial and coronal are prescribed relative to the sacrum. **Protocol for Spine:** Sag T1, T2 FSE no fat sat, STIR, FOV 28 / Ax T1 and T2 FSE (no fat sat), FOV 20.

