Study design and Methodology	This is a single-centre, open label, PoC, Phase II study. Patients who have signed the informed consent and are eligible to participate in the study will undergo the following assessments: 
 
• At screening visit, eligible and consented patients who have clinical suspicion or confirmed diagnosis of SpA will undergo a physical examination, vital signs (systolic and diastolic blood pressure, heart rate), blood analysis [CBC with automated differential, general chemistry panel (SMA-20) including CRP, PT/PTT, INR (international normalized ratio for PT values), assessment of anti-annexin V-128 antibodies] and urinalysis. In addition, disease activity score assessments (BASDAI, BASFI, BASMI and MASES) will also be performed. Screening laboratory assays, physical examination and vital signs will be performed 24 hours to 14 days before 99mTc-rhAnnexin V-128 imaging. Within 14 days of 99mTc-rhAnnexin V-128 scanning patients will undergo T1 and STIR without contrast Magnetic Resonance Imaging (MRI) of the sacro-iliac and lumbar spine joints.
 
• At Day 0 (the day of intravenous injection and imaging with 99mTc-rhAnnexin V-128), a dedicated lumbosacral spine and abdomen SPECT/CT starting 60 minutes after injection of tracer followed by a whole body planar scan and spot views on selected areas will be performed. The same SPECT/CT and whole body planar scans will be repeated at 2 hrs after injection of tracer except the spot views unless they suggest to be repeated. Vital signs assessment will also start 15 minutes before and for 2 hours after injection of radiotracer.
 
• At Day 1 (one day after the administration of 99mTc-rhAnnexin V-128), 15\20 patients will be contacted over the phone for assessment of possible adverse events (e.g. allergic reaction such as rash, edema). 5
 

Study Protocol
-----------------------

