4.3.3.2 Efficacy assessments

4.3.3.2.1 Imaging

Patients will be injected intravenously with $350 \pm 10\%$ MBq of ^{99m}Tc -rhAnnexin V-128 with an 18 gauge angiocath IV and saline TKO drip set up placed in the antecubital fossa.

Bone Lumbar Spine SPECT/CT, SI SPECT/CT and abdomen SPECT/CT will be performed 60 minutes and 2 hours after injection of radiotracer followed by a whole body scan and spot views on specific areas (spot views may not be repeated at T+2 hrs if deemed unnecessary).

The Infinia™ Hawkeye 4 SPECT/CT (GE Healthcare) scanner will be used for patients with the following parameters; start at 0° , 180° rotation/detector, 64 steps, 3° per step, 30 sec per step, overall ARC 360° , (scan time = 23 minutes) 128×128 , multi-purpose collimator (Skylight) in 1x zoom mode. An attenuation and diagnostic CT scan will be performed on the lumbar spine using a 512×512 matrix, 140 keV, 2.5 mA, axial 1 sec, 5 mm slices.

Semi-quantitative assessment of inflammatory joints and abdomen will be performed in terms of TBR as well as by calculating the relative uptake in ROI/VOIs. ROI and VOI defined and used in the different scintigraphies will strictly have the same pixel size and localization and will be measured in counts.

In case a suspected anomaly is found at imaging, it would be reported to the rheumatologist and the patient's general practitioner.

A whole lumbar spine and sacro-iliac joint MRI will be performed within 14 days of ^{99m}Tc -rhAnnexin V-128 scanning using the following parameters: **SI Joint Sequences** / 3 plane localizer / Whole pelvis Coronal T1 / Whole pelvis Coronal T2 FS. Small FOV over SI Joints (~20 cm FOV): Sequences / Obl Axial T1. Obl Axial T2 FS (May use STIR or IDEAL for poor FS), Obl Coronal T1, Obl Coronal T2, FS (May use STIR or IDEAL for poor FS). Following pre/post sequences will be used to help assess for subtle sacroilitis: Obl Ax T1 FSE FS Pre / Obl Ax T1 FSE FS Post / Obl Cor T1 FSE FS Post. FOV notes: Small FOV width should be approximately from femoral head to femoral head; oblique axial and coronal are prescribed relative to the sacrum. **Protocol for Spine:** Sag T1, T2 FSE no fat sat, STIR, FOV 28 / Ax T1 and T2 FSE (no fat sat), FOV 20.

	MDL Modello	Area: 01 Documento: MDL 01.01 Revisione: 0 Data di revisione: 18/04/2013 Pagina: 18 di 85
	Statistical Analysis Plan	
ANNEXIN 03		

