6.1.2.3 Vital signs and physical examination

Vital signs data are recorded once at screening visit and twice at imaging visit (Day 0), before the injection of ^{99m}Tc-rhAnnexin V-128 and after the last imaging procedure (within 2 hrs after ^{99m}Tc-rhAnnexin V-128 injection). Physical examination data are recorded at screening visit and at Day 30. Descriptive statistics will be tabulated by measuring time for raw data and changes from baseline (screening visit); boxplots will be reported, if appropriate. For day 0, post imaging procedures values will also be compared with pre injection counterparts (i.e. assessed on the same day). If appropriate, comparisons between different measuring times will be performed according to appropriate non-parametric paired inferential statistics. Data listing will be ordered by subject and measuring time.

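### Do a SPECT scan time that disagrees with its own settings and a two-hour limit on post-imaging vital signs call for a change to the plan?

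*Protocol*

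**What the plan says.** **Scan time.** Protocol 8.5 (Imaging) specifies 180° of rotation per detector and then "64 steps, 3° per step, 30 sec per step, overall ARC 360°, (scan time = 23 minutes". SAP 4.3.3.2.1 repeats the settings, including "scan time = 23 minutes".

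**Imaging schedule.** Protocol 8.5: "Bone Lumbar Spine SPECT/CT, SI SPECT/CT and abdomen SPECT/CT will be performed 60 minutes and 2 hours after injection of radiotracer", with a planar scan after it. The Protocol synopsis (Study design and Methodology) agrees: "The same SPECT/CT and whole body planar scans will be repeated at 2 hrs after injection of tracer". Footnote 4 to the visit schedule (Protocol Table 1; also SAP 4.3.4) allows 15 to 20 minutes for the planar scan and 5 minutes for each spot view.

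**Day 0 vital signs after injection.** Three descriptions coexist:
- Protocol 8.2 and SAP 4.3.3.3: "at the end of the last imaging procedure at Day 0", with no upper limit in hours.
- Protocol synopsis and SAP 4.3.4: "Vital signs assessment will also start 15 minutes before and for 2 hours after injection of radiotracer".
- SAP 6.1.2.3: "after the last imaging procedure (within 2 hrs after" injection. The same section adds that "post imaging procedures values will also be compared with pre injection counterparts".

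SAP 6.1.14 (Visit windows) sets no window for Day 0 vital signs.

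**What will be reported.** SAP 6.1.1 says the efficacy endpoints will not be addressed because the study stopped early. SAP 8 limits the output to subject listings after closure at 5 patients.

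**The concern.** The scan time is printed next to the settings that should produce it, and the product is wrong. Regions of interest are measured in counts, and counts depend on how long the camera dwells at each position. A reader might therefore doubt how the images were acquired.

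The vital-sign rule in SAP 6.1.2.3 cannot be satisfied as written: a reading taken after imaging that starts at 120 minutes cannot fall within 120 minutes. This is the only post-injection reading, and it is the one set against the pre-injection value. If the 2-hour limit were enforced, a reading taken at the end of imaging would be late. A reading taken inside 2 hours would not fit the listing's post-imaging heading. Whether a patient counted as on time would then depend on which section was consulted.

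**Working it through.** **1. Scan time.** Inputs from Protocol 8.5 and SAP 4.3.3.2.1: 64 steps, 3° and 30 s per step, 180° per detector, 360° overall, 23 min stated. Scan time = steps × seconds per step / 60.

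| Reading of the settings | Calculation | Minutes |
|---|---|---|
| Steps as printed | 64 × 30 / 60 | 32 |
| Steps from 180° / 3° = 60 | 60 × 30 / 60 | 30 |
| Single head, 360° / 3° = 120 | 120 × 30 / 60 | 60 |
| 64 views shared by two heads = 32 stops | 32 × 30 / 60 | 16 |

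The stated 23 min is not reproduced by any of these. The last reading also fails on coverage, since 32 × 3° = 96°, short of 180°. To obtain 23 min one needs 23 × 60 / 30 = 46 steps, or 23 × 60 / 64 = 21.6 s per step. If 64 steps and 30 s are right, the printed time is 32 − 23 = 9 min short (9 / 32 = 28%). The documents do not show which figure is wrong. The angle mismatch is smaller: 64 × 3° = 192° against 180°, which rounding of 180 / 64 = 2.81° could explain.

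**2. Does any result use the printed time?**
- The primary endpoint (Protocol 10.9, SAP 6.1.1.2) is a visual 0 to 3 grade against background uptake. Duration does not enter.
- A target-to-background ratio takes both regions from the same acquisition, so dwell time cancels.
- The count method (Protocol 10.9, SAP 6.1.1.3) subtracts background, corrects for physical decay and takes a geometric mean of anterior and posterior counts. The printed SPECT duration is not an input.
- Decay over the disputed 9 min, using the 6.02 h half-life in Protocol 7.2 (361.2 min), is 1 − 2^(−9/361.2) = 1.7%.
- The dwell time actually used does affect counts, but that is fixed by the scanner at acquisition, not by the figure in the text.

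**3. End of the 2-hour imaging set.** End = 120 + SPECT time + planar time, with SPECT 23 to 32 min and planar 15 to 20 min. CT, repositioning and spot views are left out, so these are lower bounds.
- Planar scan alone: 120 + 15 = 135 to 120 + 20 = 140 min.
- One SPECT plus planar: 120 + 23 + 15 = 158 to 120 + 32 + 20 = 172 min.
- Three separate SPECT acquisitions (lumbar, sacroiliac, abdomen) plus planar: 120 + 69 + 15 = 204 to 120 + 96 + 20 = 236 min.

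Every case passes 120 min. The documents do not settle whether the set is one acquisition or three: Protocol 8.5 names three regions and SAP 11.4(3) derives a separate time for each.

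**4. Does the vital-sign analysis depend on it?** The comparison in SAP 6.1.2.3 pairs a pre-injection with a post-imaging value. The pairing is unaffected by the parenthesis, and SAP 8 reduces the output to listings in any case. Even if an exact sign or signed-rank test were run on 5 pairs, its smallest two-sided p-value would be 2 × (1/2)^5 = 0.0625, above the 5% level in SAP 6.1.4.

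**5. Can a reader see what happened?** The shells give injection time (Listing 16.2.5.1/1), imaging date and time (Listing 16.2.6.1), and vital-sign date and time with a time-point label (Listing 16.2.9.3). The interval from injection to each reading follows by subtraction.

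**The case for a change.** The strongest case for acting is that listings are now the whole output, so a listing should not rest on a rule that cannot be met. SAP 6.1.11 lists protocol deviations by subject, and a reading might be classed as late or on time according to the section applied. The minutes-from-injection variable in SAP 11.4(3) also has no column in the imaging shell, and reconciling the text costs little.

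Part of this stands. The contradictions exist, and no generous reading removes either of them. The consequences do not follow, for three reasons:

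- **Deviations.** SAP 6.1.11 concerns departures from the protocol. The limit tied to the post-imaging reading is in a descriptive sentence of the SAP. Protocol 8.2 sets no such limit, and the synopsis sentence can be read as an observation period. No passage says that readings after 2 hours will be flagged.
- **Listing column.** SAP 11.4 already sends derived variables to listings or tables, and the shells show both clock times. The variable covers imaging times only, so a column would settle neither the scan duration nor the vital-sign timing.
- **Counts.** A shorter dwell would lower counts, but correcting a printed figure would not alter images already acquired.

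**Conclusion.** Two separate clerical inconsistencies. The 23-minute scan time is 7 to 9 minutes below what the settings most directly give (30 or 32 minutes). The 2-hour limit in SAP 6.1.2.3 is overrun by at least 15 minutes (planar scan alone), by about 38 to 52 minutes with one SPECT, and by about 84 to 116 minutes with three.

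The passages contradict one another. If either document is reissued, the sponsor must reconcile the acquisition settings with the scan time, and the Day 0 vital-sign timing across the synopsis, Protocol 8.2 and SAP 4.3.3.3, 4.3.4 and 6.1.2.3. Which setting or timing is right is not for this review to say.

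No change to the design or analysis follows. Neither figure feeds an endpoint, a sample size, a test or the continuation decision. Editing the text would not alter what the trial did or can conclude. This rests on two assumptions: that the listings are produced as their shells show, with actual times, and that output stays limited to listings for 5 patients as SAP 8 states. One limit remains: the imaging shell carries a single time per scan and does not say whether it is the start or the end, so scan duration itself cannot be read from the listings.
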